## 4.0 Study Intervention(s)/Interaction(s)

#### 4.1 Description:

Before the intervention, the study design with use of hypothetical scenarios will be explained to the participant. The concept of randomization will be also be explained. The participants will be asked a few questions to assess their understanding of the study design, specifically the hypothetical nature of the scenarios. We will also assess whether they understand the concept of being randomized to see one

website first and then the other. Only those participants that understand the study design will be invited to participate in the intervention and will be randomized. For subjects that are randomized, a survey will be administered verbally to collect demographic information and information about their kidney disease and comorbidities. The functional health literacy and numeracy assessment and health status questionnaire will be completed. Subjects will be stratified by the transplant center site and then block randomized. One group will be shown the existing SRTR website with its existing SRTR report cards and then the website with the new patient-centered AHRQ report cards for kidney transplants. The other group will be shown the two websites in opposite order. Each participant will have at most 30 minutes to view each of the websites. After viewing each website, responses to the intervention will be collected. Sessions where participants are reviewing the websites will be recorded using Zoom. Figure 2 shows the study design whereby subjects will be block randomized once to one of the four groups consisting of 18 subjects each. At the end of the study, the patients will have access to both the websites.

The study interventions can be administered in person on a laptop. During the COVID-19 pandemic, the intervention can be administered remotely via email and zoom. The link to the websites will be sent via encrypted email and the intervention will be recorded via zoom. The recordings for subjects at Hennepin Healthcare will be stored on computers at that site.

If participant does not have your own electronic device or internet, the study will send the participant a study iPad with internet that participant can use for the intervention and then to send back to the study team. We will provide detailed instructions on how to use the iPad and Zoom application. The study will also pay for a FedEx pick up from the participants' home to return the iPad to the study team after the completion of the intervention.

Figure 2: Study Design of the Randomized Trial.

**Study Design** 36 subjects per organ type randomized to see 36 Subjects per organ type randomized to see SRTR website first AHRQ website first. 18 subjects (30 min) 18 subjects (30 min) 18 subjects (30 min) 18 subjects (30 min) Primary Outcome: Which **Primary Outcome: Primary Outcome:** Primary Outcome: Which Which of the following Which of the following of the following transplant of the following transplant transplant centers have transplant centers have centers have the most centers have the most the most experience with experience with the most experience with experience with transplanting candidates transplanting candidates transplanting candidates transplanting candidates over age 70? with BMI over 40? over age 70? with BM! over 40? Then subject will see Then subject will see SRTR Then subject will see Then subject will see AHRQ website. (30 min) SRTR website. (30 min) website. (30 min) AHRQ website. (30 min) Primary Outcome: Which Primary Outcome: Which Primary Outcome: Which **Primary Outcome:** of the following transplant of the following transplant Which of the following of the following transplant centers have the most centers have the most transplant centers have centers have the most experience with experience with the most experience with experience with transplanting candidates transplanting candidates transplanting candidates transplanting candidates over age 70? over age 70? with BMI over 40? with BMI over 40?

#### **Procedures Involved**

- 5.1 Study Design: This aim will entail an RCT of kidney transplant candidates at HHS transplant centers to evaluate the new report card.
- 5.2 Study Procedures: The study entails assessing knowledge and perceived value of information along with measure of satisfaction with decision-making and decisional conflict. Open-ended questions that provide feedback on the sites will also be collected at the end of the study procedures. This study involves one study visit, approximately 90 minutes in length, to review the two report card websites. This study visit will be done in person or online using Zoom.

The first 5 participants at each site will be enrolled in a vanguard study to optimize the study design. If no change in study design is required, these subjects will be analyzed in the main study.

For consented patients who will be participating in the study remotely, the study team will contact patients via email to confirm the patient's email address. If participants do have their own electronic device with good internet connection, the study team will send a Zoom link for the Zoom testing session to check patient technology and ability to share their screen.

If a participant is willing to participate but has any issues with internet connection or/and missing or inadequate electronic device, the study team will send the participant a study iPad with internet that participant can use for the intervention

5.0

and then to send back to the study team. We will provide detailed instructions on how to use the iPad and Zoom application. The study will also pay for a FedEx pick up from the participants' home to return the iPad to the study team after the completion of the intervention.

When the clinical coordinator confirms good technology connection (through patient personal electronic device or study iPad). The study coordinator will schedule a 90 minute Zoom study visit. A sample script for the day of this study visit is attached.

If a participant prefers a face to-face study visit and this is allowed based on local site guidelines, the study intervention can be administered in the clinic. A study coordinator will help patients to work on study's iPad and record the Zoom session of the visit.

We estimate that the total time for the study visit will be around 90 min. After viewing each website, responses to the intervention will be collected.

- 5.3 Follow-Up: Data that will be collected includes demographic information, information regarding participants' kidney disease and other comorbidities, and the recordings of the study sessions during which participants evaluate the two report card websites. Following the study intervention, there is no follow up for this study.
- 5.4 Individually Identifiable Health Information: This study will involve use of individually identifiable health information. All subjects will sign a HIPAA authorization form separate from the consent form.

## 6.0 Data Banking

- 6.1 Storage and Access: The identifiers for all Hennepin Healthcare subjects will be stored at Hennepin Healthcare. The recordings will be banked for future use for 5 years after the study is completed and stored at the respective sites. The PI and the study team will have access to the de-identified data and the recordings.
- 6.2 Data: The identifiers collected with the initial survey will be destroyed at the end of the study.
- 6.3 Release/Sharing:

Data will only be accessed by researchers involved in this study and designated lab personnel. The Principal Investigators, will be responsible for the confidentiality of banked data.

## 7.0 Sharing of Results with Participants

N/A - No assessments are performed that may be shared with participants.

## 8.0 Study Duration

8.1 Each participant will be enrolled in the study and the duration anticipated to enroll all study participants is two years. The duration anticipated to complete all study procedures and data analysis is seven years.

## 9.0 Study Population

- 9.1 Inclusion Criteria: All adults seeking a kidney transplant are eligible for the RCT. We will focus on recruiting kidney waitlist candidates.
- 9.2 Exclusion criteria are inability to speak or understand English, visual impairment, and inability to give consent. All vulnerable populations except for those listed in the table titled vulnerable populations, will be excluded.
- 9.3 Screening: Screening will be done by viewing potential participants' information in their electronic medical record (Epic). The research coordinator at Hennepin Healthcare will have access to Epic at HHS and File MakerPro. Within Epic, researchers will first look at a potential subjects 'Patient Type' to determine if the he or she has opted in or opted out of research.

If the patient has opted in to research, preliminary screening will take place before initial approach.

If the patient has opted out of research, the researcher will not contact the patient via mail for recruitment. If the opt-out patient has an appointment at HHS, they may be approached in-clinic, by the treatment team, per clinic guidelines.

Patients will be approached either in-person, by mail (followed up via a phone call) or by encrypted email if the study is first presented by the care team and the patient wishes to learn more about the study (see section 12.1). Allowing for these approaches for recruitment enables us to reach more than just the newly waitlisted patients (those who are in for appointments more frequently) and ensures a wider net of patient availability.

Before the intervention, the study design with use of hypothetical scenarios will be explained. The concept of randomization will be also be explained. The participants will be asked a few questions to assess their understanding of the study design, specifically the hypothetical nature of the scenarios. One such sample question is: In one of the scenarios being tested, a 71 year old candidate is looking to find a transplant center that transplants patients like him or her. So how old is the person that is looking for information about transplant centers? "

We will also assess whether they understand the concept of being randomized to see one website first and then the other. The participants will be asked a question to assess their understanding of the randomization process. One such sample question is: Can you tell me how it will be decided which patients in this study get to see the SRTR website first and which will get to see the AHRQ website first?

Only those participants that understand the study design as denoted by giving the correct answers to the screening questions will be invited to participate in the intervention and will be randomized.

#### 10.0 Vulnerable Populations

# 10.1 Vulnerable Populations:

Vulnerable Population	
Population / Group	Identify whether any of the following populations will be targeted, included (not necessarily targeted) or excluded from participation in the study.
Children	Excluded from Participation
Pregnant women/fetuses/neonates	Excluded from Participation
Prisoners	Excluded from Participation
Adults lacking capacity to consent and/or adults with diminished capacity to consent, including, but not limited to, those with acute medical conditions, psychiatric disorders, neurologic disorders, developmental disorders, and behavioral disorders	Excluded from Participation
Non-English speakers	Excluded from Participation
Those unable to read (illiterate)	Excluded from Participation
Employees of the researcher	Excluded from Participation
Students of the researcher	Excluded from Participation
Undervalued or disenfranchised social group	Included/Allowed to Participate
Active members of the military (service members), DoD personnel (including civilian employees)	Included/Allowed to Participate

Individual or group that is approached for participation in research during a stressful situation such as emergency room setting, childbirth (labor), etc.	Excluded from Participation
Individual or group that is disadvantaged in the distribution of social goods and services such as income, housing, or healthcare.	Excluded from Participation
Individual or group with a serious health condition for which there are no satisfactory standard treatments.	Excluded from Participation
Individual or group with a fear of negative consequences for not participating in the research (e.g. institutionalization, deportation, disclosure of stigmatizing behavior).	Excluded from Participation
Any other circumstance/dynamic that could increase vulnerability to coercion or exploitation that might influence consent to research or decision to continue in research.	Excluded from Participation

# 10.2 Additional Safeguards:

This is a study that is open to all kidney transplant candidates who fit study inclusion/exclusion criteria. All vulnerable populations except for those listed in the table above will be excluded.

# 11.0 Number of Participants

## 11.1 Number of Participants to be Consented

The table shows the required sample size for ranges of detectable differences and within-person correlation.

						Correlation			
							0.		
		0.0	0.1	0.2	0.3	0.4	5	0.6	
Ī	0.20	107	98	89	79	67	56	45	

Detectable	0.22	90	82	76	66	56	47	38	
Difference	0.24	76	71	64	55	48	40	33	
	0.25	70	66	59	51	44	37	*	
	0.26	66	61	55	48	41	34	*	
	0.28	57	53	46	41	35	30	*	
	0.30	51	45	41	36	32	27	*	

On the conservative side, we will power the study to detect a proportional difference as small as 25% and therefore plan to enroll at 72 subjects for each organ trial. Recruitment will continue until this desired sample size is achieved. Given the low-risk nature of this project, there will be no stoppage rules based on interim analysis for recruitment.

This 72 is in addition to the 130 subjects enrolled in the interviews and focus groups and usability testing. Thus the total enrollment will be 130 + 72 = 202. The 97 subjects already enrolled along with the 50 subjects that can be enrolled in the trial at HCMC, brings the total maximum enrollment to 147 at HCMC.

#### 12.0 Recruitment Methods

#### 12.1 Recruitment Process:

The research coordinators will screen kidney transplant candidates at HHS until an appropriate number have agreed to participate. Patients may be recruited a number of ways:

- Patient direct contact at the Hennepin Healthcare transplant clinic or hospital - the study coordinator will ascertain an appropriate time to introduce the study to the patient during a standard of care visit and ask if they are interested and willing to participate in the study. If they agree to learn more, the investigator or study team member will close the door and in the presence of family (if requested), begin the consent process.
- By mail alternately, eligible patients will be sent an invitation letter along with consent materials by mail. The invitation letter will state that they are being invited to the study because they are a transplant candidate at the Hennepin Healthcare. A study coordinator will then contact the patient by phone to introduce the study and ask if they are interested and willing to participate after allowing time for the invitation letter to arrive. Patients will be instructed to sign and return the consent materials by mail if they wish to participate in the study.
- Electronically if waiver of consent not provided by IRB- Patients may be consented electronically using an e-consent platform (REDcap HHRI) with an accompanying phone call or video feed to conduct the consent conversation. The subject will review the e-consent in detail and have the chance to ask questions. Study personnel will then ask the subject questions to ensure that

they understand the information presented in the consent discussion using a teach back method.

By care team - If allowed by local sites, care team members may ask
potential participants if they are interested in learning more about this study
by email. If so, the study team may send potential participants the study
invitation letter by encrypted email.

The research coordinator will keep a log of all participants who do not meet eligibility criteria and why. The coordinator will assess whether the participant has a smartphone, tablet or computer through which the participant can access the websites being studied.

Patients who agree to participate in the study will be consented and randomized. All participants will read, sign, and date a consent form before undergoing any study procedures. A copy of the signed consent form will be given to the participant. Patients who are consented by mail will not be considered as enrolled in the study until the study team has received their signed consent form. The consent process will be ongoing until recruitment goals are met.

#### 12.2 Source of Participants:

The sites for the RCT include HHS. Participants will be recruited from the adult kidney transplant candidate.

#### 12.3 Identification of Potential Participants:

Potential participants will be recruited based on information from their medical record—they must be kidney transplant candidates with either evaluations or waitlisted at the HHS. All potential patients under the care of the Hennepin Healthcare use an EMR that will be accessed to screen for adult patients. During the chart review, patients meeting exclusion criteria will be excluded. All potential transplant candidate participants are patients of the Hennepin Healthcare.

All members of the research team have access to Epic. The research team will run a report for potential participants who meet inclusion/exclusion criteria for the study. An eligibility report may be generated by FileMaker and EPIC that have similar information for kidney transplant candidates.

The study coordinators will create a patient list to evaluate possible participants against inclusion and exclusion criteria. Coordinators will exclude patients who have declined to participate in research, unless this study is presented by the care team and the patient wishes to learn more about the study.

While preparing invitation letters, the study team may review the list to determine if some potential participants are coming into clinic for routine care. If a potential participant is coming into clinic for routine care, the study team may approach the potential participant in clinic.

#### 12.4 Recruitment Materials:

An IRB-approved recruitment letter will be sent to potential participants recruited via mail. An IRB-approved phone script will also be used to contact potential participants after the recruitment letter is sent. No recruitment materials (other than the IRB-approved consent form) will be used for potential participants recruited in person.

12.5 Payment: Participants will receive a \$40 Target e-gift card or check for their participation. Parking costs will be covered for patients participating in the in-person study visits.

#### 13.0 Withdrawal of Participants

#### 13.1 Withdrawal Circumstances:

If a subject is unable or unwilling to complete the study tasks (interventional testing), they may be withdrawn from the study without their consent.

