## 3.0 Study Endpoints/Events/Outcomes

- 3.1 Primary Endpoint/Event/Outcome: The primary outcomes are two separate assessments of the comprehension of the report card. To assess comprehension, the correct response to the following type of question will be assessed, "Which of the following transplant centers have the most experience with transplanting candidates over age 70?" There will be one correct answer; respondents will be told to assume they are in a specific zip code or state and are over age 70 and then asked to choose one of the several transplant center report cards shown or respond "Don't know." Another example of the question used to assess comprehension will be used, "Which of the following transplant centers have the most experience with transplanting candidates with body mass index (BMI) over 40?" There will be one correct answer; respondents will be told to assume they are in a specific zip code or state and have a BMI over 40 and then asked to choose one of the several transplant center report cards shown or respond "Don't know." Similar measures used previously by [name], to determine the best way to present report cards to the general public (17). We will also determine comprehension of key concepts in the reports, to identify participants' ability to determine whether a center performs transplants on "patients like me."
- 3.2 Secondary Endpoint(s)/Event(s)/Outcome(s): Perceived value of information will be determined via patient responses to the following question, "How useful is the information in the report card in helping you choose a transplant center for you or your family?" Response choices to the questions will be based on a 5-point Likert-type scale (Example: 1 = not at all useful to 5 = very useful). We will also measure satisfaction with decision-making and decisional conflict using the effective decision subscale of the Ottawa Decisional Conflict Scale, which has been validated in multiple studies (18-21).

These questions will be written on cards if the intervention is conducted face-to-face. If conducted via HIPPA compliant zoom call, the questions will be placed in the chat box for the subject to refer to them during the intervention.

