## 17.3 Statistical Analysis:

The primary analysis will be based on the conservative "intention-to-treat" (ITT) approach. We will use a chi-square test and logistic regressions for analyzing primary and secondary measures. A sensitivity analysis will be conducted excluding subjects that did not enter the correct hypothetical information into the website. The research coordinator will record the amount of time subjects spend with each website and the webpages viewed by each subjects and that information will be analyzed for descriptive analysis. Other subset analysis will be conducted but presented as ad hoc analysis.

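### Does the plan need a stated rule for primary answers never given by subjects withdrawn during the website tasks?

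*Combined protocol and SAP*

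**What the plan says.** Section 13.1 gives staff a participation rule: "If a subject is unable or unwilling to complete the study tasks (interventional testing), they may be withdrawn from the study without their consent". Section 4.1 puts randomization after the understanding check and before the surveys and the websites ("For subjects that are randomized, a survey will be administered verbally to collect demographic information and information about their kidney disease and comorbidities"), so a withdrawal for not finishing the tasks falls after randomization.

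On analysis, 17.3 states "The primary analysis will be based on the conservative" intention-to-treat approach, and then "We will use a chi-square test and logistic regressions for analyzing primary and secondary measures". Its one named sensitivity analysis concerns wrong scenario details entered into the website, not absent answers. Section 13.2 allows continued use of data already collected, but speaks only of subjects who withdraw consent. Missing-data texts appear in the reference list, but 17.1 cites them only for propensity-based covariate adjustment.

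On the outcome, 3.1 says "The primary outcomes are two separate assessments of the comprehension of the report card". Each question has one correct answer, and *Don't know* is an allowed response. On the session, 5.2 says "This study involves one study visit, approximately 90 minutes in length, to review the two report card websites" and 4.1 says "Each participant will have at most 30 minutes to view each of the websites". Subjects are "block randomized once to one of the four groups consisting of 18 subjects each".

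**The concern.** A chi-square test or logistic regression uses only outcomes that have a value. The intention-to-treat label says who is analysed, not what value an absent answer takes. A routine software run could therefore omit such answers while the report still says intention-to-treat.

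The reason for the loss also matters here. Being unable to finish a website task can itself be a failure to understand the website, which is the endpoint. Omitting those answers could remove failures from the harder website and narrow the difference. Other patterns of loss would widen it. With 36 answers per question and website, a few omissions might seem enough to change a conclusion.

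**Working it through.** **The plan's own figure.** No stated figure is in dispute. The table in 11.1 and 17.2 gives 70 for a difference of 0.25 at correlation 0.0, and the plan enrolls 72. Alpha, power and baseline rate are not stated. One back-fitted set comes close: two-sided 5%, 90% power, paired proportions 0.225 and 0.475. The discordant proportion is 0.225×0.525 + 0.475×0.775 = 0.486, and n = (1.960+1.282)² × (0.486 − 0.0625)/0.0625 = 71.2, rounded up to 72. The table is plausible but cannot be verified. It is indexed by within-person correlation, so the powered comparison is between websites within subjects.

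**Inputs.** There are 72 subjects (17.2) in four groups of 18 (4.1). Figure 2 is broken in the text, but each question appears to be asked of half the subjects on each website. That gives 72 answers per website pooled and 36 per question. The target difference is 25 points (17.2). Assumed: the correct rates, the number of missing answers, a two-sided 5% level and an unpaired test.

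**Widest possible effect on a rate.** With m answers missing on one website, best case minus worst case is m/72 pooled or m/36 per question.

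| m | pooled | per question |
|---|---|---|
| 1 | 1.4 points | 2.8 points |
| 2 | 2.8 points | 5.6 points |
| 4 | 5.6 points | 11.1 points |

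**Pooled test.** X² = (difference)² / [p(1−p)(1/n₁+1/n₂)], where p is the overall correct rate.
- 27/72 v 45/72: 0.25² / [0.25 × 2/72] = 9.0, p = 0.003.
- 4 not-correct answers omitted on the existing website (27/68): 22.8 points, p = 0.007.
- 12 omitted (27/60): p = 0.044. 13 omitted (27/59): p = 0.055.
- With continuity correction, the first p above 0.05 comes at 11 omitted (27/61): p = 0.054.

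Thirteen of 72 is 18%, and eleven is 15%, all on one website and all not correct.

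**One question alone.**

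| existing v new | difference | uncorrected p | continuity-corrected p |
|---|---|---|---|
| 14/36 v 23/36, nothing missing | 25.0 | 0.034 | 0.059 |
| 14/34 v 23/36, two not-correct omitted | 22.7 | 0.057 | 0.096 |
| 12/34 v 23/36, two correct omitted | 28.6 | 0.017 | 0.031 |

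Fisher's exact test also gives 0.059 for the first row. With correction, a gap of 9/36 starts above 0.05 for every existing-website count from 9 to 18. Two omissions cross 0.05 without correction at counts 11 to 19, so the two ranges largely overlap.

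**Effect of the scoring convention.** Counting an absent answer as not correct leaves 14/36 v 23/36 at 25.0 points if those answers would have been not correct. The convention has a cost of its own. Suppose four subjects stop on the existing website shown first and never open the new one, and k of them would have been correct there. Scored as not correct, the pooled difference is (18−k)/72, or 25.0 down to 19.4 points. Treated as missing, it is (45−k)/68 − 27/72, or 28.7 down to 22.8 points. Neither convention is uniformly closer to 25.0.

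**Loss of precision.** Assume 37.5% v 62.5%, correlation 0 and a two-sided 5% level. Paired power is Φ[(0.25√n − 1.96√0.531)/√0.469]: 84.4% at n = 72 and 80.3% after a 10% loss (n = 64.8).

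**How often an answer would be absent.** The 30-minute cap limits viewing. Responses are taken after viewing, so a subject who runs out of time can still be asked and can answer *Don't know*. Two full viewings use 60 of about 90 minutes and leave 30 for the rest. Subjects are screened for understanding (9.3), remote connections are tested first (5.2), and there is no follow-up (5.3). The first five subjects at each site form a vanguard (5.2) that could expose completion problems. Sessions are recorded and reviewed (14.1, 17.4), so a reason for stopping could be checked later.

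**The case for a change.** The case for a rule is fair. Withdrawal under 13.1 is discretionary, and the person running the session sees which website is open. No section says what value an absent answer takes. The per-question reading has support in 3.1. A first-website-only reading is just as sensitive: 18/36 v 27/36 gives p = 0.028, and leaving out two absent answers in the existing-website-first group (18/34) gives p = 0.054. A subject who stops after one website also loses the within-person pair. Closing the gap would cost only wording.

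What stands is that the text is silent and that the choice could in principle be made after the data are seen. What does not stand is the step from silence to omission, because no section says such answers or subjects leave the analysis. The first-website example is also fragile before any loss, with a continuity-corrected p of 0.0515. A finer rule, scoring inability as not correct but unwillingness as missing, is no clear gain. A subject frustrated by a hard website may be recorded as unwilling, and the judgement would fall to a coordinator who knows which website is in use.

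**Conclusion.** This is a gap that analysts fill sensibly, and no change to the plan is called for. Read together, 3.1 and 17.3 point to one ordinary analysis: all randomized subjects kept, answers already given used, and an unanswered primary question counted as not correct. The alternative treatment would be shown if any case occurs. A plan followed in that way gives a sound result.

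The size supports this. Pooled, one to four absent answers move a website's rate by at most 1.4 to 5.6 points, and it takes 13 one-sided omissions (11 with continuity correction) to lose significance at a 25-point difference. The per-question result can turn on two answers, but only under an uncorrected, unpaired test, and for most baseline rates where that happens the corrected test is already above 0.05. All of this rests on assumed counts and correct rates, and on the 36-per-question layout read from a broken figure. The documents give no withdrawal rate, so the actual bias cannot be estimated. If withdrawals proved common or clearly tied to one website, this conclusion would need another look.
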